13. SPECIMEN BANKING

- *If specimens will be banked for future research, describe where the specimens will be stored, how long they will be stored, how they will be accessed and who will have access to the specimens*
- *List the information that will be stored with each specimen, including how specimens are labeled/coded*
- *Describe the procedures to release the specimens, including: the process to request release, approvals required for release, who can obtain the specimens, and the information to be provided with the specimens.*

N/A

14. DATA MANAGEMENT AND CONFIDENTIALITY

- *Describe the data and specimens to be sent out or received. As applicable, describe:*
 - *What information will be included in that data or associated with the specimens?*
 - *Where and how data and specimens will be stored?*
 - *How long the data will be stored?*
 - *Who will have access to the data?*
 - *Who is responsible for receipt or transmission of data and specimens?*
- *Describe the steps that will be taken to secure the data during storage, use and transmission.*

Imaging data will be stored on a secure laptop sourced specifically for use in this study. This laptop will require an advanced graphics card and CPU to accommodate for the vast amount of data processed by the device. Software for processing and visualizing the 3D model will be pre-loaded into the laptop. Only study personnel will have access to this laptop. Additional data may be obtained from the subject's EMR. This will include but not limited to: demographics, past medical history, past radiologic findings, etc. Data will be stored on a password protected REDCap database accessible only to research personnel. Data will be stored for 7 years.

--

15. DATA AND SAFETY MONITORING PLAN

A specific data and safety monitoring plan is only required for greater than minimal risk research. For guidance on creating this plan, please see the [Guidance Document on the HRPP website](#).

*Part I – this part should be completed for all studies that require a DSMP.
 Part II – This part should be completed when your study needs a Data and Safety Monitoring Board or Committee (DSMB/C) as part of your Data and Safety Monitoring Plan.*

Part I: Elements of the Data and Safety Monitoring Plan

- *Indicate who will perform the data and safety monitoring for this study.*
- *Justify your choice of monitor, in terms of assessed risk to the research subject's health and well being. In studies where the monitor is independent of the study staff, indicate the individual's credentials, relationship to the PI, and rationale for selection*
- *List the specific items that will be monitored for safety (e.g. adverse events, protocol compliance, etc)*
- *Indicate the frequency at which accumulated safety and data information (items listed in # above) will be reviewed by the monitor (s) or the DSMB/C.*
- *Where applicable, describe rules which will guide interruption or alteration of the study design.*
- *Where applicable, indicate dose selection procedures that will be used to minimize toxicity.*
- *Should a temporary or permanent suspension of your study occur, in addition to the IRB, indicate to whom will you report the occurrence.*

N/A

Part II: Data and Safety Monitoring Board or Committee

- *When appropriate, attach a description of the DSMB.*
- *Provide the number of members and area of professional expertise.*
- *Provide confirmation that the members of the board are all independent of the study.*

N/A

16. WITHDRAWAL OF SUBJECTS

- *Describe anticipated circumstances under which subjects will be withdrawn from the research without their consent*
- *Describe procedures for orderly termination*
- *Describe procedures that will be followed when subjects withdraw from the research, including partial withdrawal from procedures with continued data collection.*

We do not anticipate any circumstances in which a subject will be withdrawn from the research without their consent. Once the ultrasound testing is complete, in-person participation is done. We will continue to collect data from the subject's medical record for the next 6 months. If subjects choose not to participate with the study, they will undergo their prescribed ultrasound testing but no 3D data will be recorded.

--

17. RISKS TO SUBJECTS

- *Describe any potential risks and discomforts to the subject (physical, psychological, social, legal, or other) and assess their likelihood and seriousness and whether side effects are reversible. Where appropriate, describe alternative treatments and procedures that might be advantageous to the subjects.*
- *Include risks to others , like sexual partners (if appropriate)*

- *Discuss why the risks to subjects are reasonable in relation to the anticipated benefits and in relation to the importance of the knowledge that may reasonably be expected to results*
- *Describe the procedures for protecting against or minimizing any potential risks, including risks to confidentiality, and assess their likely effectiveness.*

There are no additional physical risks to subjects participating in this study. The device in question attaches to the ultrasound probe. The participant will undergo a standard ultrasound exam to evaluate their vasculature. The ultrasound technologist will not perform any specific or unique testing maneuvers for the sake of the device. The ultrasound technologist will be performing the standard of care ultrasound exam, and the device will create 3D images of the vasculature based on the ultrasound exam. The patient and ultrasound technologist do not have to do anything differently. The only risk in this study is breach of confidentiality. All precautions and procedures will be undertaken to prevent such an occurrence. Only study personnel will have access to the data which will be under password protection. This minimal risk is appropriate for the potential knowledge gained by obtaining a 3D image of the subject's diseased vasculature

18. RESEARCH RELATED HARM/INJURY

- *Describe the availability of medical or psychological resources that subjects might need as a result of anticipated problems that may be known to be associated with the research.*
- *If the research is greater than minimal risk, explain any medical treatments that are available if research-related injury occurs, who will provide it, what will be provided, and who will pay for it.*

This is a minimal risk study. The participant will face no greater risk than those posed by undergoing ultrasound testing for vascular diseases.

19. POTENTIAL BENEFIT TO SUBJECTS

- *Explain what benefits might be derived from participation in the study, noting in particular the benefit over standard treatment (e.g. a once-a-day administration instead of four times a day, an oral formulation over an IV administration).*
- *Also state if there are no known benefits to subjects, but detail the value of knowledge to be gained*

The subject has the potential to have immediate impact from participation. They will be able to view the 3D rendering of their vasculature and their clinician will be able to highlight areas of vascular disease if any. The ability to view the disease process in a 3D model of their own vessels might increase compliance with

treatment (i.e. demonstrating stenosis of a vessel). This is a more detailed and informative picture than what is provided by standard ultrasound studies.

20. PROVISIONS TO PROTECT PRIVACY INTERESTS OF SUBJECTS

- *Describe the methods used to identify potential research subjects, obtain consent and gather information about subjects to ensure that their privacy is not invaded.*
- *In addition consider privacy protections that may be needed due to communications with subjects (such as phone messages or mail).*

Potential research subjects will be identified from the patient pool scheduled to undergo ultrasound testing at the wound center. Participant data will not be collected until the subject is consented. Study personnel will not have to communicate with subjects once their imaging study is complete.

21. COSTS TO SUBJECTS

- *Describe any foreseeable costs that subjects may incur through participation in the research*
- *Indicate whether research procedures will be billed to insurance or paid for by the research study.*

Participants will not incur any costs for enrolling in the study.

22. PAYMENT TO SUBJECTS

- *Describe the amount of payment to subjects, in what form payment will be received and the timing of the payments.*

Participants will not be compensated for enrolling in the study.

23. CONSENT PROCESS

If obtaining consent for this study, describe:

- *Who will be obtaining consent*
- *Where consent will be obtained*
- *Any waiting period available between informing the prospective participant and obtaining consent*
- *Steps that will be taken to assure the participants' understanding*
- *Any tools that will be utilized during the consent process*

- *Information about how the consent will be documented in writing. If using a standard consent form, indicate such.*
- *Procedures for maintaining informed consent.*

Consent will occur prior to the participant undergoing their ultrasound testing. The consenting will be performed by the PI or study coordinators when the patient is in the vascular suite. This is a private area where the patient will be able to ask questions and/or raise any concerns. The standard Northwell Health minimal risk consent form template will be utilized.

In the state of NY, any participants under the age of 18 are considered children. If your study involves children, additional information should be provided to describe:

- *How parental permission will be obtained*
- *From how many parents will parental permission be obtained*
- *Whether permission will be obtained from individuals other than parents, and if so, who will be allowed to provide permission. The process used to determine these individual's authority to consent for the child should be provided*
- *Whether or not assent will be obtained from the child*
- *How will assent be documented*
- *Whether child subjects may be expected to attain legal age to consent to the procedures for research prior to the completion of their participation in the research. If so, describe the process that will be used to obtain their legal consent to continue participation in the study. Indicate what will occur if consent is not obtained from the now-adult subjects.*

N/A

If the study involves cognitively impaired adults, additional information should be provided to describe:

- *The process to determine whether an individual is capable of consent*
- *Indicate who will make this assessment*
- *The plan should indicate that documentation of the determination and assessment will be placed in the medical record, when applicable, in addition to the research record.*
- *If permission of a legally authorized representative will be obtained,*
 - *list the individuals from who permission will be obtained in order of priority*
 - *Describe the process for assent of subjects; indicate whether assent will be required of all, some or none of the subjects. If some, which subjects will be required to assent and which will not.*
 - *If assent will not be obtained from some or all subjects, provide an explanation as to why not*
 - *Describe whether assent will be documented and the process to document assent*

- *Indicate if the subject could regain capacity and at what point you would obtain their consent for continued participation in the study*

N/A

If the study will enroll non-English speaking subjects:

- *Indicate what language(s) other than English are understood by prospective subjects or representatives*
- *Indicate whether or not consent forms will be translated into a language other than English*
- *Describe the process to ensure that the oral and written information provided to those subjects will be in that language*
- *If non-English speaking subjects will be excluded, provide a justification for doing so*

Spanish consents will be made available for potential subjects who are Spanish-speaking.
--

24. WAIVER OR ALTERATION OF THE CONSENT PROCESS

N/A

Complete this section if you are seeking an alteration or complete waiver of the consent process.

- *Describe the possible risks of harm to the subjects involved in this study and explain why the study involves no more than minimal risk to the subject:*
- *Explain why the waiver/ alteration will not adversely affect the rights and welfare of subjects*
- *Explain why it is impracticable to conduct this research if informed consent is required*
- *Explain why it is not possible to conduct this research without using the information or biospecimens in an identifiable form*
- *If appropriate, explain how the subjects will be provided with additional pertinent information after participation. If not appropriate to do so, explain why.*

In regards to the RETROSPECTIVE COHORT:

This study poses minimal risk of harm to subjects within this cohort as the intervention to be studied has already occurred. The subject consented to undergoing the vascular study at that time. Our research team will access these subject charts to collect information regarding the results and outcomes of these subjects after their vascular studies were performed.

The waiver of consent will not adversely affect subject's rights and welfare because there is no clinical intervention and/or assessment being made on these subjects. The intervention in question has already been performed on the

subject to which they consented to at the time of the procedure. Inclusion in the study will not affect their care in any form.

Requiring informed consent for this cohort would be impracticable because many subjects who qualify for this cohort are no longer under the care of the researchers. In addition, tracking down and locating these subjects in order to have a consent form delivered and signed would create a significant logistical challenge. Finally, the creation of a consent form would then create the only traceable paper trail linking the subjects to the study. All other records of these subjects are digitized and will be accessed via EMR.

Identifiable information is required to perform the data collection. To ensure accuracy and quality of the data, subject records may be accessed more than once. Once the data collection phase is complete, all identifiers will be permanently erased from the database. The final dataset to be analyzed will not contain any PHI.

Subjects in this cohort will not be provided with any information after participation because no findings will directly affect their care. They have already undergone ultrasound testing. Any findings from our study will have no direct benefit to subjects within this cohort.

Complete this section if you are obtaining informed consent but you are requesting a waiver of the documentation of consent (i.e., verbal consent will be obtained). To proceed with a waiver based on these criteria, each subject must be asked whether they wish to have documentation linking them to this study. Only complete subsection 1 OR subsection 2.

SUBSECTION 1

- *Explain how the only record linking the subject to the research would be the consent document.*
- *Explain how the principal risk of this study would be the potential harm resulting from a breach in the confidentiality*
- *Indicate whether or not subjects will be provided with a written statement regarding the research.*

N/A

SUBSECTION 2

- *Describe the possible risks of harm to the subjects involved in this study and explain why the study involves no more than minimal risk.*
- *Confirm that the research only involves procedure for which consent is not normally required outside the research context.*
- *Indicate whether or not subjects will be provided with a written statement regarding the research.*

N/A

25. WAIVER OF HIPAA AUTHORIZATION

N/A

Complete this section if you seek to obtain a full waiver of HIPAA authorization to use and/or disclose protected health information.

- *Describe the risks to privacy involved in this study and explain why the study involves no more than minimal risk to privacy:*
- *Describe your plan to protect identifiers from improper use or disclosure and to destroy them at the earliest time.*
- *Indicate why it is not possible to seek subjects' authorization for use or disclosure of PHI.*
- *Indicate why it is not possible to conduct this research without use or disclosure of the PHI.*
- *Indicate if PHI will be disclosed outside NSLIJ Health System, and if so, to whom.*
Note: PHI disclosed outside NSLIJ Health System, without HIPAA authorization needs to be tracked. Please see guidance at www.nslij.com/irb for information about tracking disclosures.

In regards to the RETROSPECTIVE COHORT:

This study involves the use of data from clinical records. Patient identifiers are only needed for accurate data acquisition and tracking of outcomes. Once the data is completely abstracted, it will be de-identified. Patient privacy is protected by the anonymity of the data.

All data will be handled by only the study staff responsible for abstraction. After that it will be de-identified. Data will be stored on password protected databases housed on institutional servers. Only research personnel will have access to the database. Once accuracy of the data is verified, subjects will be assigned study IDs, and identifiers will be deleted.

Identifiers are used only during the abstraction period to access the medical records to conduct the study.

Consent to use PHI is not possible as this study only requires PHI to track and obtain additional data from Northwell EMR. Once data collection is complete, all PHI will be destroyed from the database. No PHI will be disclosed to third parties.

PHI is required to locate additional information from subject EMR.
No PHI will be disclosed to outside 3rd parties.

Complete this section if you seek to obtain a partial waiver of the patient's authorization for screening/recruitment purposes (i.e., the researcher does not have access to patient records as s/he is not part of the covered entity)

Note: Information collected through a partial waiver for recruitment cannot be shared or disclosed to any other person or entity.

- *Describe how data will be collected and used:*
- *Indicate why you need the PHI (e.g. PHI is required to determine eligibility, identifiers are necessary to contact the individual to discuss participation, other)*
- *Indicate why the research cannot practicably be conducted without the partial waiver (e.g. no access to medical records or contact information of the targeted population, no treating clinician to assist in recruitment of the study population, other)*

--

26. VULNERABLE POPULATIONS:

Indicate whether you will include any of these vulnerable populations. If indicated, submit the appropriate appendix to the IRB for review:

- Children or viable neonate*
- Cognitively impaired*
- Pregnant Women, Fetuses or neonates of uncertain viability or nonviable*
- Prisoners*
- NSLIJ Employees, residents, fellows, etc*
- poor/uninsured*
- Students*
- Minorities*
- Elderly*
- Healthy Controls*

If any of these populations are included in the study, describe additional safeguards that will be used to protect their rights and welfare.

N/A

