8. NUMBER OF SUBJECTS

- *Indicate the total number of subjects to be accrued locally. If applicable, distinguish between the number of subjects who are expected to be pre-screened, enrolled (consent obtained), randomized and complete the research procedures.*
- *If your study includes different cohorts, include the total number of subjects in each cohort.*
- *If this is multisite study, include total number of subjects across all sites.*

The total number of subjects we plan to enroll is 270. We plan to enroll 135 subjects into the 3D imaging cohort of this study. Another 135 patients will be identified retrospectively for the historical cohort.

The sample size calculation was based on the primary outcome of 30-day readmission. We assumed a readmission rate of 10% in the 2D group and a readmission rate of 2% in the 3D group. We would need 135 patients in each group to have 80% and a confidence level of 95% to detect this difference.

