10. ENDPOINTS

- *Describe the primary and secondary study endpoints*
- *Describe any primary or secondary safety endpoints*

The primary endpoint of the study will be the treatment outcomes for the patients. We will review readmission rates (30 days from the day of the ultrasound) as well as compliance to first follow-up appointment after the ultrasound of interventional cohort. These endpoints will be compared to those of a historical cohort of persons who were treated for similar pathologies in the past.

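### Both outcomes are collected from patient records by a research team that can see the cohort, and the readmission result rests on about 16 expected events

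*Protocol*

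**What the plan says.** Section 10 names the two outcomes: "We will review readmission rates (30 days from the day of the ultrasound) as well as compliance to first follow-up appointment after the ultrasound". It gives no rule for which hospital stays count, or for how a rescheduled or clinic-cancelled visit is classified.

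Both outcomes come from patient records:

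- **2D cohort.** Section 24 has the research team open the charts to collect results and outcomes. Section 25 adds "All data will be handled by only the study staff responsible for abstraction". That sentence is a privacy statement about the retrospective cohort only, but it confirms that study staff do the abstraction.
- **3D cohort.** Section 9 provides for EMR review over six months after the scan, and Section 16 says "We will continue to collect data from the subject's medical record for the next 6 months".

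Section 7 limits the 2D cohort to scans in calendar 2019, while the 3D cohort is consented and scanned prospectively. Section 4 states a directional hypothesis: better attendance and fewer readmissions with 3D. No section describes masking of whoever collects the outcomes.

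On data quality, Section 24 says "To ensure accuracy and quality of the data, subject records may be accessed more than once", and Section 25 ties deletion of identifiers to the data having been verified. Both statements are made for the retrospective cohort. For the 3D cohort, Sections 11 and 14 cover storage and access.

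**The concern.** Anyone who opens a dated record knows which cohort it belongs to, and the team knows which result is hoped for. An admission is fairly objective once defined, but the protocol leaves some decisions to the reader: whether a given stay counts, and which appointment is the first follow-up. If those decisions lean differently in the two cohorts, even slightly and without intent, the comparison absorbs the difference as a treatment effect. The regression adjustment in Section 12 deals with baseline differences and cannot remove a difference in how outcomes were counted.

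What makes this worth fixing is the small number of events. With few readmissions expected, especially in the 3D cohort, a handful of classification decisions can move the primary test across its threshold.

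**Working it through.** **Inputs.** From Section 8: "We assumed a readmission rate of 10% in the 2D group and a readmission rate of 2% in the 3D group"; "80% and a confidence level of 95% to detect this difference", which I read as 80% power and two-sided alpha 0.05 (sidedness is not stated); "We plan to enroll 135 subjects into the 3D imaging cohort of this study"; "Another 135 patients will be identified retrospectively for the historical cohort". From Section 12: chi-square test on the proportion readmitted. I use it without continuity correction.

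**1. The plan's own sample size.** Normal approximation with unpooled variance:

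n = (1.960 + 0.842)² × (0.10×0.90 + 0.02×0.98) / (0.10 − 0.02)² = 7.849 × 0.1096 / 0.0064 = 134.4, rounded up to 135.

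The stated 135 per group reproduces. The pooled-variance version gives 138.

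**2. Expected readmissions.** 135 × 0.10 = 13.5 in 2D and 135 × 0.02 = 2.7 in 3D, so 16.2 in total.

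**3. How many reclassified patients change the result.** With a events in 2D, b in 3D and 135 per group:

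χ² = 270 (a − b)² / [(a + b)(270 − a − b)], significant above 3.841.

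| 2D v 3D | χ² | p |
|---|---|---|
| 13 v 3 | 270×100/(16×254) = 6.644 | 0.010 |
| 13 v 4 | 270×81/(17×253) = 5.085 | 0.024 |
| 13 v 5 | 270×64/(18×252) = 3.810 | 0.051 |
| 14 v 3 | 270×121/(17×253) = 7.596 | 0.006 |
| 14 v 5 | 270×81/(19×251) = 4.586 | 0.032 |
| 14 v 6 | 270×64/(20×250) = 3.456 | 0.063 |
| 10 v 3 | 270×49/(13×257) = 3.960 | 0.047 |
| 9 v 3 | 270×36/(12×258) = 3.140 | 0.076 |

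Starting from 13 v 3, two more 3D readmissions remove significance; from 14 v 3, it takes three. If only the 2D count moves, 13 must fall to 9, which is four patients (five from 14).

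**4. False benefit if 3D admissions are undercounted.** Suppose both true rates are 10% and a fraction u of 3D admissions is not counted, so the recorded 3D rate is 0.10 × (1 − u). Summing the exact binomial probabilities of every table with p<0.05 and fewer events in 3D gives:

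| u (assumed) | Recorded 3D rate | Probability of a false 3D benefit |
|---|---|---|
| 0% | 10.0% | 2.5% |
| 5% | 9.5% | 3.5% |
| 10% | 9.0% | 4.7% |
| 20% | 8.0% | 8.3% |
| 30% | 7.0% | 14.1% |

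The documents give no value for u, so the table shows a range. Neither calculation applies to follow-up attendance, for which the protocol states no expected rates.

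**The case against.** The strongest reply is that the documents show no actual bias. Fragility to two or three patients comes from small counts and would exist with perfect ascertainment. The undercount is hypothetical, and at 5 or 10% the effect is modest. Abstraction rules and masking of chart readers are also often placed in an abstraction manual or analysis plan, which is not at hand. All of this stands and limits the strength of the point. It does not remove it: the protocol itself fixes the source and the collectors, and its two scan periods make the cohort visible in any dated record. Unequal ascertainment cannot be repaired at the analysis stage.

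A reader might infer more than the text supports in four ways:

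- **That the 2D cohort gets extra checking.** The repeat-access and verification wording sits in the waiver sections, which are answered only for the retrospective cohort because only that cohort needs a waiver. It explains why identifiers are needed and when they are deleted. It does not set up a quality-control step for one cohort, and six months of 3D record review may also involve repeated access.
- **That the direction of bias is known.** Checking can remove wrongly counted events as well as find missed ones.
- **That the people who recruit also abstract.** Section 23 names the investigator or study coordinators for consent, and Section 25 refers to staff responsible for abstraction. Nothing says they are the same people.
- **That records are necessarily read by hand.** This is a reasonable reading of abstraction and chart access, but the protocol does not say it.

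**Conclusion.** The point holds as a weakness in how the outcomes are ascertained. Both outcomes are collected by the research team from records that reveal the cohort, under a directional hypothesis and without stated rules for which stays and visits count. With 16.2 readmissions expected at the protocol's own rates, two to three patients classified differently in 3D decide significance.

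The false-benefit range of 3.5% to 14.1%, against 2.5% with no undercount, rests on equal true rates of 10%, an undercount of 5 to 30% that affects 3D only, and an uncorrected chi-square test at two-sided 0.05. It shows how sensitive the test is and does not predict what will happen. The protocol does not establish that undercounting will occur or that the cohorts will be checked unequally. This is an inexpensive improvement to the primary comparison; the weakness does not by itself invalidate the study.

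**What to change.** In Sections 10 to 12, state that both outcomes are taken from one structured EMR query run identically for the two cohorts. It would return:

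- any inpatient encounter dated within 30 days of the scan; and
- the recorded status of the first wound-center appointment after the scan, such as completed, missed, cancelled or rescheduled.

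State one classification rule for these fields and one accuracy check, each applied in the same way to both cohorts. The waiver text in Sections 24 and 25 needs no change. The rule should be settled before abstraction starts, because those sections have identifiers deleted once 2D data collection is complete, which may rule out a later re-read.

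**Cost.** A report request and a few lines of protocol text, with no extra patients. Coded fields may miss detail that a reader would find in the notes, although the same rule would then apply to both cohorts. The query also depends on the site's EMR holding these fields. Section 24 indicates that the retrospective subjects' records are digitized and reached through the EMR, but the protocol does not describe the fields available.
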